The role of antibiotics on child growth is unclear. Recent studies indicate that antibiotic use could impact child growth, but a previous study in Niger failed to find a statistically significant correlation between antibiotic treatment with azithromycin and stunting, underweight, or MUAC of pre-school aged children. Longitudinal studies have been recommended to further investigate the role of antibiotics on child growth⁶. Meanwhile some studies suggest antibiotics may create modifications in the gut microbiota impacting nutrient absorption and weight gain⁷. We propose to measure child growth through anthropometric measurements longitudinally over a 6-month period to see if azithromycin treatment impacts child development. We hypothesize that children receiving a dose of azithromycin will have more growth and development in terms of height, weight, and mid-upper arm circumference compared to children who receive placebo.

We propose a longitudinal study designed to improve our knowledge about the changes in the intestinal microbiome following the course of a single dose of antibiotic in a setting with high childhood mortality and morbidity. More specifically, we propose to follow 450 children for a 6-month time period that are between the ages of 8 days old and 59 months old. Children in this age bracket are at the highest risk for mortality from infectious causes, and furthermore, they are at the highest risk for malnutrition. This group of children would receive the greatest benefit from this intervention. The causal changes in the microbiome are vastly understudied in regards to changes in the gut microbiome following a course of antibiotics. We hypothesize that children receiving a dose of azithromycin will have a higher prevalence of anti-pneumococcal bacterial resistance in nasopharyngeal samples, decreased bacterial diversity, and a higher likelihood of identification of bacterial resistance genes in stool and nasopharyngeal samples.

3 Chapter 3: Study Design

We propose to prospectively follow 1500 children treated with azithromycin or placebo for 6 months in the town of Nouna. Our goal is to evaluate intestinal microbiome changes and child growth longitudinally. We will individually randomize eligible children to a single dose of

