3.2 Sample Size

We will enroll up to 1500 children into the two study arms (725/arm). In the sub-study, 25 children per arm will be randomized. This sample size is based on the primary outcome, Simpson's alpha diversity in the intestinal microbiome. We will base some statistical assumptions on preliminary data from the Nouna HDSS. For instance, we assume a 15% loss to follow-up, a baseline effective number of 9, and a standard deviation of 0.7.

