2.1 Planned Analyses

2.1.1 Longitudinal Trial

Four hundred fifty children between the ages of 8 days and 59 months may be enrolled in the trial and be offered placebo or azithromycin in a masked fashion. Relevant indicators will be collected using whole blood venipucture, nasopharyngeal swabs, fresh frozen stool, rectal swabs, and anthropometry measurements at days 0, 14, and 180. Children followed up within day 120 and day 240 will be included in primary day 180 analysis. Fifty randomly selected children (25 per arm) will have an additional rectal swab collected at days 2, 4, 6, 8, 10, 12 post-treatment.

Primary Analyses. Pairwise comparison of *Campylobacter*, *C. upsaliensis* and *C. hominis* using Fisher's exact test, corrected for multiple comparisons using Holm-Bonferroni method.

We will compare profile of *Campylobacter*, *C. upsaliensis* and *C. hominis* based on L_1 , L_2 distance, and PERMANOVA. We will compare diversity between arms at days 14 and 180 separately, using Shannon's Index and Simpson's Index.

Statistical considerations.

- Model adequacy will be checked by examination of residuals or other goodness of fit tests as needed. Inadequate model fit will prompt us to report alternative models.
- Multiple imputation will be used in case of missing baseline covariates (if applicable). Missing outcome variables will be handled by sensitivity analysis and reporting of conditional results.
- False Discovery Rate will be calculated for each estimated significant effect.

Secondary analyses.

Note that participants outside of WHO Child Growth Standards for WAZ (-6 to +5 SD), HAZ (-6 to +6 SD), or WHZ (-5 to +5 SD) will be excluded from all anthropometric analyses.

S. pneumoniae carriage and macrolide resistance Separate Fisher's exact test at days 14 and 180.

lytA occurence Separate Fisher's exact test at days 14 and 180.

erm B, mef A, pp2A Separate Fisher's exact test at days 14 and 180.

N. meningitides, H. influenzae, Moraxella, S. aureus Pairwise comparison of organisms using Fisher's exact test, corrected for multiple comparisons using Holm-Bonferroni method.

PERMANOVA of L_1 and L_2 distance of bacterial reads. Shannon's and Simpson's estimated gamma diversities will be compared by arm.

Malaria Fisher's exact test of parasitemia and clinical malaria at days 14 and 180.

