- weight gain Defined as grams per kilogram per day (g/kg/day) will be compared between arms separately at days 14 and 180 using linear regression. Baseline weight is accounted for in our metric of weight gain and will not be included in the regression analysis. We will use ordinary least squares method of estimatation and permutation tests to estimate coefficient p-values.
- HAZ, WAZ, WHZ, MUAC As secondary analysis, we will perform separate ANCOVA of anthropometric indicators at days 14 and 180, adjusting for baseline.

3 Sample Size Considerations

We assume a mean (standard deviation) alpha Shannon's index of 16.47 (7.12) using results from Thuy et al. [DAR⁺17]. Assuming 80% power and detectable effect size of 1.02 standard deviations and no loss to follow-up, we propose a sample size of 225 per group, totaling 450 study participants.

4 Randomization

The randomization will be conducted using R. The function sample with option replace=FALSE will be used to conduct the random shuffling. Note that the choice of the random number seed completely determines the randomization. To ensure the integrity of the randomization, we will use the procedure we used for MORDOR/Malawi.

Samples will be randomly grouped into 5-pools for processing, within an arm and a time point.

5 Abbreviations

ANCOVA Analysis of covariance

- $\mathbf{DSMC}\,$ Data and Safety Monitoring Committee
- ${\bf HAZ}$ height for age Z score
- MUAC Mid upper arm circumference
- ${\bf SAP}\,$ Statistical Analysis Plan
- \mathbf{WAZ} weight for age Z score
- \mathbf{WHZ} weight for height Z score

References

[DAR⁺17] T. Doan, A. M. Arzika, K. J. Ray, S. Y. Cotter, J. Kim, R. Maliki, and et al. Gut microbial diversity in antibiotic-naive children after systemic antibiotic exposure: A randomized controlled trial. *Clinical Infectious Disease*, 64, 2017.

6 Revision History

- 29 May 2019 Revised specification and wording of primary and secondary outcomes. Moved weight gain to secondary outcome. Clarified Bonferroni correction for certain species.
- 13 Jan 2020 Updated the pre-specified sample size for the sub-section of GAMIN sample (GAMIN QOD).
- 16 Jan 2020 Abbreviated the study name on title page.
- 20 Mar 2020 Added sample size considerations section and specification of day 180 time window.
- 08 May 2020 Specified WHO standard range for inclusion for anthropometric (child growth) analysis.
- 02 Jul 2020 Increased upper range of day 180 window from day 210 to day 240.

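### SAP 3's sample-size inputs do not fit together: 1.02 SD at 80% power needs about 16 to 17 children per arm, not 225, and N, loss and sizing index differ from Protocol 3.2

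*SAP*

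**What the plan says.** SAP 3 (Sample Size Considerations) sizes the trial on a Shannon "index of 16.47 (7.12) using results from" a cited earlier study, that is, a mean of 16.47 and an SD of 7.12. With 80% power it then states a "detectable effect size of 1.02 standard deviations and no loss to follow-up, we propose a sample size of 225 per group", 450 in total. It gives no alpha and no sidedness. The only alpha in the SAP is 0.001, in the Introduction, for analyses that were not specified.

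SAP 2.1.1 repeats the total: "Four hundred fifty children between the ages of 8 days and 59 months may be enrolled in the trial". On the analysis it says "We will compare diversity between arms at days 14 and 180 separately", with Shannon's and Simpson's indices, but names no test. SAP 4 adds that samples are processed in pools of five within arm and time point.

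Protocol 3.2 gives another basis: "We will enroll up to 1500 children into the two study arms (725/arm"), sized on Simpson's alpha diversity, where "we assume a 15% loss to follow-up, a baseline effective number of 9, and a standard deviation of 0.7". It states no effect size, power or alpha. Elsewhere the protocol carries both totals. Section 2.1 says "we propose to follow 450 children for a 6-month time period", and the opening of Chapter 3 says "We propose to prospectively follow 1500 children treated with azithromycin or placebo for 6 months".

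**The concern.** A difference of one SD is large, and a two-arm comparison of means needs few children to detect it. A figure of 225 per arm beside 1.02 SD and 80% power therefore looks wrong at sight: the effect, its unit or the N comes from some other calculation.

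The detectable effect tells a reader how sensitive the diversity comparison is. Diversity is the outcome on which Protocol 3.2 sizes the trial, and SAP 2.1.1 lists it under the primary analyses. As printed, the detectable difference is 1.02 × 7.12 = 7.26 units, 44% of the assumed mean of 16.47, so the trial appears able to find only very large shifts. If the slip is in the unit, the error runs the other way and the claimed 80% power is not there. In addition, the two documents do not say how 450 and 1500 relate, so neither gives a complete basis for the planned N.

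**Working it through.** **Inputs.** From SAP 3: power 80%, effect 1.02 SD, SD 7.12, mean 16.47, no loss, 225 per arm. From Protocol 3.4: 1:1 allocation. From Protocol 3.2: 725 per arm and 15% loss. Assumed, because neither document states it for sizing: two-sided alpha of 5%, with other values shown.

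**Step 1. Try to reproduce 225.** For a two-sample comparison of means, n per arm = 2(k/d)², with k = z(1−α/2) + z(0.80) = 1.960 + 0.8416 = 2.8016.

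- d = 1.02: n = 2 × (2.8016/1.02)² = 15.09, so 16 per arm.
- t-test: 16.11, so 17 per arm (power 79.7% at 16 and 82.2% at 17).

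The stated 225 is not reproduced.

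**Step 2. Vary what SAP 3 leaves open.**

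| Reading | Per arm |
|---|---|
| One-sided 5% | 12 (normal), 13 (t) |
| Two-sided 0.001 | 33 (normal), 36 (t) |
| Rank test, assumed relative efficiency 0.864, two-sided 5% | 18 (normal), 19 (t-based) |
| Baseline-adjusted, assumed correlation 0.3 to 0.7, two-sided 5% (normal) | 13.7 to 7.7 before rounding |
| Pool of 5 as the unit, two-sided 5% | 16 to 17 pools = 80 to 85 children |
| Pool of 5, two-sided 0.001 (t) | 36 pools = 180 children |
| Pool of 5, two-sided 0.001, rank efficiency 0.864 | 35.56/0.864 = 41.2, so 42 pools = 210 children |

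For 225 children to be the exact requirement, z(1−α/2) = 1.02 × √(225/2) − 0.8416 = 9.977, a two-sided alpha of about 2 × 10⁻²³. No reading tried gives 225.

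**Step 3. What 225 per arm detects.** Detectable effect = k√(2/n), with the child as unit and an unadjusted comparison. For 15% loss, n is 225 × 0.85 = 191.25 or 725 × 0.85 = 616.25.

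| Alpha | 225 | 225 less 15% | 725 | 725 less 15% |
|---|---|---|---|---|
| One-sided 5% | 0.234 | 0.254 | 0.131 | 0.142 |
| Two-sided 5% | 0.264 | 0.287 | 0.147 | 0.160 |
| Two-sided 0.0125 (illustrative: two indices, two days) | 0.315 | 0.341 | 0.175 | 0.190 |
| Two-sided 0.001 | 0.390 | 0.423 | 0.217 | 0.235 |

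At two-sided 5% and SD 7.12, 225 per arm detects 0.2641 × 7.12 = 1.88 units, which is 11% of 16.47. After 15% loss it is 0.2865 × 7.12 = 2.04 units. The ratio to the printed effect is 1.02/0.2641 = 3.86. At 225 per arm a rank test (efficiency 0.864) detects 0.284 SD, and baseline adjustment (correlation 0.3 to 0.7) detects 0.252 to 0.189 SD.

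**Step 4. A possible slip of unit (query only).** If 1.02 is in index units, d = 1.02/7.12 = 0.1433. Power at 225 per arm is Φ(0.1433 × √112.5 − 1.960) = 33%, and 80% power needs 765 per arm. At 725 per arm the power would be about 78%, and at 750 about 79%.

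**Step 5. The two documents side by side.**

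| | SAP 2.1.1 and 3 | Protocol 3.2 |
|---|---|---|
| N | 450 (225 per arm) | up to 1500 (725 per arm) |
| Loss | none | 15% |
| Sizing index | Shannon | Simpson |
| Assumed level (SD) | 16.47 (7.12) | 9 (0.7) |
| Effect size and power | 1.02 SD, 80% | not given |

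The protocol's 725 per arm makes 1450; adding the 25 per arm of the rectal swab group makes 1500. Protocol 4.6 reports baseline malaria rapid tests in 407 + 43 = 450 children in November 2019. The revision histories date the protocol's increase to 18 March 2020 and the addition of SAP 3 to 20 March 2020, and SAP version 1.7 still has 450. This suggests that 450 is a first cohort, but neither sample-size section says so.

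**The case against.** The strongest reply is that 225 per arm does give at least 80% power for 1.02 SD; power is essentially 100%. The SAP only proposes the number, so the sentence fails as an equality and not as a floor. That is true, but a detectable effect at 80% power is an equality by definition, and the printed one does not belong to this N.

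It can also be said that calling the effect 3.9 times too large presumes that N is right. If 1.02 is in index units, the label is wrong, and the 765 per arm then needed lies close to the protocol's 1500 in total. This stands as a caution: 0.264 SD is conditional on 225 children per arm, and only the sponsor can say which input slipped.

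Pooling with a strict alpha and a rank test comes nearest, at 210. But 0.001 is reserved for unspecified analyses, and the SAP's revision history dates pooling to October 2021, after SAP 3 was written.

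Two further points stand in part. SAP 2.1.1 plans both indices, so 16.47 against 9, and SDs of 7.12 against 0.7, may only reflect different indices or scales; the firm conflict is in which index sizes the trial. And the 450 rapid tests are weak evidence on enrolment, because Protocol 4.6 ties that test to fever.

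Finally, a null result is read chiefly from its confidence interval, so this is a correction of the record. That limits the importance of the point but does not make the sentence right.

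**Conclusion.** The concern holds. At 80% power and two-sided 5%, 1.02 SD calls for 16 to 17 children per arm, and no alpha, test or unit tried yields 225. With 225 children per arm as independent units, no loss and an unadjusted comparison, the detectable difference is 0.264 SD (1.88 units), so the printed effect is about 3.9 times too large. If index units were meant, it is the 80% power that is wrong, at about 33%. If the pool is the unit, the 1.88 figure may not apply, because the documents give no between-pool SD.

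The SAP and Protocol 3.2 also conflict in current text on N, loss and sizing index. The alpha is assumed throughout, but the mismatch does not depend on it. The damage is confined to the design justification: no estimate, test or interval changes, and the mismatch alone does not show that the trial is too small. It should be fixed.

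**What to change.** 1. **SAP 3.** Find the calculation behind 225, and replace the 1.02 SD statement with the detectable effect for the confirmed N, alpha and sides, loss, diversity test and unit. If the sponsor confirms 225 children per arm, an unadjusted two-sample comparison and no loss, the text can read: *With 225 children per arm, 80% power, two-sided alpha of 5% and no loss to follow-up, the detectable difference is 0.26 standard deviations (1.88 units at SD 7.12).* With 15% loss it is 0.29 SD (2.04 units). If 1.02 was meant in index units, say so and restate power at 225 per arm as about 33%. Record the change in the SAP's revision history as a later restatement.
2. **SAP 2.1.1, SAP 3, Protocol Chapter 2 and Protocol 3.2.** Make N, index and scale, SD and loss agree, and say whether 450 is a first cohort of up to 1500. In Protocol 3.2 give the effect size, power and alpha behind 725 per arm. For reference, at two-sided 5% and 80% power that N detects 0.147 SD, or 0.160 SD after 15% loss.
3. **Unit of analysis.** State whether it is the child or the five-sample pool. If the pool, recalculate with the number of pools and a sourced between-pool SD.

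The cost is wording in four places and the sponsor's confirmation of the inputs, plus a between-pool SD if pools are the unit. No added enrolment is called for.
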